10.1 Safety Estimands

The estimands used for the safety objectives, outlined in **Section 4.2.3**, and the methods for analysing the data are described further in this section.

10.1.1 Data Point Sets and Intercurrent Events

The DPS (which outline the population used) and intercurrent event strategies used for all safety estimands can be found in **Table 9**.

Table 9: Data Point Sets and Intercurrent Event Strategies for the Safety Estimands

Estimand	DPS	Lack of compliance with the vaccine administration schedule (vaccine administration outside of required time window)	Use of concomitant medications or other vaccines
Safety estimands	DPS3	Treatment Policy Strategy: Any safety data taken after vaccine administration outside of the correct time window will be used as collected	Treatment Policy strategy: Data will be used as collected

10.1.2 Analysis Methods

A safety estimand will be created for all of the AE outputs outlined below. Analyses will be completed for the two country subgroups defined in **Section 7.4** and overall.

Summary tables will contain counts of subjects, percentages of subjects in parentheses and the number of events or descriptive statistics, where applicable.

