5.1.3 Safety Objective

The safety objective is to evaluate the safety profile of a 2-dose regimen of HIL-214 co-administered with routine pediatric vaccines at 4 and 6 months of age, compared to that of the routine pediatric vaccines co-administered with placebo.

This objective will be assessed using data collected for the solicited reactions (AEs; for 7 days [including day of administration] after each dose of trial vaccine), unsolicited AEs (for 28 days [including day of administration] after each dose of trial vaccine and routine vaccine), serious adverse events (SAEs) and AEs leading to trial withdrawal (from first dose of trial vaccine to 12 months of age), medically-attended adverse events (MAAEs; from first dose of trial vaccine to 28 days post-dose 2) and AEs leading to vaccine withdrawal (from first dose of trial vaccine to planned administration of the second dose at 6 months of age).

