13.1.3 Safety Analysis

All safety summaries will be provided for each trial arm and overall.

Solicited reactions:

Solicited reactions will be assessed 30 minutes after administration of each dose of trial vaccine, and then daily for 7 days (including the day of administration). For each solicited reaction, the number and percentage of subjects who experienced an event will be computed, for each day from Day 1 to Day 7 post-dose (including the day of dose) and overall.

Solicited reactions will be summarized by severity. For subjects with more than 1 episode of the same event within an interval, the maximum severity will be used for tabulations.

Body temperature measurements will be summarized in categories (including fever, defined as temperature $\geq 38^{\circ}\text{C}$), without adjustment for the route of measurement. Summaries of the day of first onset of each event and the number of days subjects experienced each event will also be provided.

Data from the 30 minutes assessment of solicited reactions immediately post-vaccination will be summarized separately.

Unsolicited AEs:

Any unsolicited AEs, SAEs, MAAEs, and AEs leading to trial vaccine, routine vaccine or trial withdrawal, will be coded using MedDRA, and summarized by system organ class (SOC) and preferred term (PT) using number and percentage of subjects with an AE. Subjects with more than one occurrence for the term will be counted only once for this term. Unsolicited AEs will be collected up to 28 days after administration of each dose of trial vaccine and routine vaccine (including the day of administration); summaries will also be provided by event severity (mild, moderate, severe) and relationship (not related, related) to trial vaccine, routine vaccine or trial procedures. For subjects with more than one AE within an SOC or a PT, the AE with the maximum severity or strongest relationship within each SOC and each PT will be included in the summaries by severity or relationship, respectively.

Any unsolicited AEs will be summarized in the following 3 time intervals: 1) overall up to 28 days after each dose (including the day of administration), 2) with onset between 1 and 7 days after each dose (including the day of administration), and 3) with onset between 8 and 28 days after dose (including the day of administration).

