4.2.3 Safety Endpoints and Estimands

Population:

Same as for the primary immunogenicity estimands.

Treatment strategies to be compared:

- At least one dose of HIL-214, with concomitant routine pediatric vaccines.
- At least one dose of placebo, with concomitant routine pediatric vaccines.

Safety endpoints:

- Occurrence (yes/no) of solicited local and systemic reactions during the first 7 days (including day of administration) after each dose of trial vaccine, overall and by severity.
- Occurrence (yes/no) of any unsolicited AE during the first 28 days (including day of administration) after each dose of trial vaccine, overall, by severity and by relatedness.
- Occurrence (yes/no) of SAEs, MAAEs, AEs leading to vaccine or trial withdrawal, during the corresponding collection periods, overall, by severity and by relatedness.

Population level summaries:

Percentages of subjects reporting specific events, overall, by severity and by relatedness, for each trial arm.

The analysis methods for the safety endpoints used in the safety estimands are outlined in **Section 10.1.2.**

Intercurrent events strategies:

Lack of compliance with the routine and trial vaccine administration schedule, and use of concomitant medications and other vaccines will be handled according to the treatment policy strategy, i.e., collected AE data will be used regardless of whether or not these events occurred.

Rationale:

The safety estimands aim to evaluate the safety outcomes in pediatric subjects that receive all at least one dose of childhood vaccines or HIL-214.

5 Study Methods

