5.4 Statistical Analysis Methods

5.4.1 Difference in Percentages

The difference in percentage, given by the difference between the proportion of subjects in the vaccine group, p_2 , with the event and placebo group, p_1 , with the event is calculated using the following formula:

$$\text{Difference in percentage} = (p_2 - p_1) * 100 = \left(\frac{E_2}{n_2} - \frac{E_1}{n_1} \right) * 100 \quad (1)$$

where E_1 and E_2 are the number of events in the placebo and vaccine groups respectively, and n_1 and n_2 are the number of subjects in the placebo and vaccine groups respectively with a valid assessment.

The 95% confidence intervals for the differences in percentages will be computed using the Miettinen and Nurminen (MN) [2] method. The following formula is used for the MN CI:

$$\text{MN CI} = \left((\hat{p}_2 - \hat{p}_1) \pm Z_{1-\frac{\alpha}{2}} \sqrt{\lambda \left(\frac{\tilde{p}_2(1-\tilde{p}_2)}{n_2} + \frac{\tilde{p}_1(1-\tilde{p}_1)}{n_1} \right)} \right) * 100 \quad (2)$$

where \tilde{p}_1 and \tilde{p}_2 are the maximum likelihood estimators for p_1 and p_2 under the null hypothesis that $p_1 - p_2 = 0$ and $\lambda = \frac{n_1+n_2}{n_1+n_2-1}$ and α is the selected level of significance. All confidence intervals for the difference in percentages outlined in this SAP will be two-sided 95% confidence intervals, i.e. with $\alpha = 0.05$.

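### The safety objective is a comparison with placebo, but the planned safety analysis reports only per-arm counts and percentages, so it does not report the excess risk compatible with the data

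*SAP*

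**What the plan says.** Protocol 5.1.3 words the safety objective as a comparison. The profile seen after two HIL-214 doses is to be judged against the other arm: "compared to that of the routine pediatric vaccines co-administered with placebo". SAP 4.1 repeats it. The safety estimand (Protocol 5.2.3, SAP 4.2.3) names two strategies for comparison, at least one dose of HIL-214 and its counterpart: "At least one dose of placebo, with concomitant routine pediatric vaccines".

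The population-level summary of that estimand is the same in both documents: "Percentages of subjects reporting specific events, overall, by severity and by relatedness, for each trial arm". Protocol 13.1.3 adds: "All safety summaries will be provided for each trial arm and overall". SAP 10.1.2 fixes the table content: "Summary tables will contain counts of subjects, percentages of subjects in parentheses and the number of events or descriptive statistics, where applicable". SAP 10.2.1 to 10.2.8 then list the outputs. These are counts and percentages by severity, relationship and time interval, summaries of onset day and duration for solicited reactions, a stacked bar plot and listings. None contains a risk difference, a ratio or a confidence interval, between arms or within an arm.

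The SAP does hold a between-arm method. Section 5.4.1 states: "The 95% confidence intervals for the differences in percentages will be computed using the Miettinen and Nurminen (MN) [2] method". Section 9.1.1.3 applies it to the binary primary immunogenicity endpoints and Section 7.5.1, reweighted, to their supplementary estimands. Nothing applies it to safety. Protocol 13.3 and SAP Section 6 declare the trial descriptive, with no power calculation.

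**The concern.** The estimand names two strategies to compare, but its summary measure describes each arm on its own. The primary immunogenicity objective is worded as the same kind of comparison, in the same descriptive trial, and there the plan reports an estimate with its uncertainty. The descriptive label explains why there are no tests, margins or power. It does not explain why one comparative objective gets an interval and the other does not.

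Protocol 4.2 says the trial is designed to support concomitant administration in the planned phase 3 efficacy trial. For that use, a reader of the safety tables needs to know how large an excess of reactions is still compatible with what was seen. Two similar percentages printed side by side do not show this.

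**Working it through.** **Is there a figure to reproduce?** No. The documents give no expected event rate, detectable difference or margin for safety. The rates below are assumptions chosen to show the scale.

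**Inputs.** 200 per arm, 1:1 (Protocol 6.1, SAP Section 6). Two-sided 95%, z = 1.96 (SAP 5.4.1). λ = 400/399 = 1.0025.

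**MN score interval.** The limits are the values δ at which

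Z(δ) = (p̂₂ − p̂₁ − δ) / √{λ[p̃₂(1−p̃₂)/n₂ + p̃₁(1−p̃₁)/n₁]} = ±1.96,

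where p̃₁ and p̃₂ are the maximum likelihood estimates under p₂ − p₁ = δ, recomputed at each δ.

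- *40 v 40 events (20% each).* At δ = 0.0789, p̃₂ = 0.2451 and p̃₁ = 0.1662. The variance is 1.0025 × (0.1850 + 0.1386)/200 = 0.001622, so the standard error is 0.0403 and 0.0789/0.0403 = 1.96. Interval: −7.9 to +7.9 points.
- *6 v 2 events (3% v 1%).* At δ = 0.0552, p̃₂ = 0.0617 and p̃₁ = 0.0065. The standard error is 0.01796, and (0.0200 − 0.0552)/0.01796 = −1.96. The lower limit is found in the same way. Interval: −0.9 to +5.5 points.
- *60 v 40 events (30% v 20%).* Interval: +1.5 to +18.4 points.
- *0 v 0 events.* Here p̃₁ = 0 and p̃₂ = δ, so δ = c/(1+c) with c = 1.96²λ/n = 3.84 × 1.0025/200 = 0.0193. Upper limit: +1.9 points.

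**US tables.** SAP 10.1.2 also reports safety by country, and the US target is at least 100 infants (Protocol 4.2). With exactly 100 split 1:1, so 50 per arm, equal 30% rates are compatible with about ±18 points. Zero events in both arms gives c = 3.84 × (100/99)/50 = 0.0776 and an upper limit of +7.2 points.

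**Does the formula printed in SAP 5.4.1 give these intervals?** It evaluates p̃₁ and p̃₂ once, under zero difference, so both equal the pooled proportion and the interval is symmetric about the estimate.

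| Events (200 per arm) | Score inversion | Formula as printed |
|---|---|---|
| 60 v 40 | 1.5 to 18.4 | 1.5 to 18.5 |
| 6 v 2 | −0.9 to 5.5 | −0.7 to 4.7 |
| 0 v 0 | upper limit 1.9 | zero width |

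For 6 v 2, the pooled proportion is 8/400 = 0.02. The half-width is 1.96 × √(1.0025 × 2 × 0.02 × 0.98/200) = 0.0275, and 2.0 ± 2.75 gives the limits shown. For 0 v 0 the pooled proportion is 0 and so is the half-width. The printed form is close enough at common rates but fails for rare events such as SAEs.

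**The case against.** The strongest reply is that the plan is consistent with itself. Both documents define the safety summary as a per-arm percentage, and the SAP delivers exactly that. A reader might infer that the SAP drops a contrast the protocol promised. It does not, because the protocol's own estimand and Section 13.1.3 ask only for summaries by arm. What remains is the mismatch, present in both documents, between a comparative objective and a summary with no contrast.

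A reader might also infer that the trial will be unable to say what excess risk the data allow. That goes too far. The tables give counts and percentages, and SAP Section 8 has columns annotated with the population size, so anyone can compute an interval afterwards. No estimate is biased and no data are lost.

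Nor do the documents call the excess reaction rate a main output. The safety objective has no primary or secondary rank, and its weight for phase 3 is an inference from the stated purpose of the trial. The trial is openly descriptive, so no test, margin or power is owed.

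All of this stands and limits the point to one of reporting. It does not remove it, since a descriptive aim is compatible with an estimate and interval, as the primary objective shows.

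**Conclusion.** The point holds as a reporting gap and a cheap improvement. The objective and estimand are comparative, and the planned safety analysis does not report the excess risk compatible with the data. With 200 per arm, equal 20% rates leave ±7.9 points, 3% against 1% leaves −0.9 to 5.5, and zero events in both arms leaves up to 1.9. These sizes rest on assumed event rates and full enrolment. The US figures also assume exactly 100 infants split evenly. They show the precision of the design and say nothing about the reaction rates to expect.

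**What to change.** In SAP 10.1.2, add the HIL-214 minus placebo difference in percentages with a two-sided 95% MN interval, overall across countries and without tests, for:

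- any, and any severe, solicited local reaction and solicited systemic reaction, per dose;
- each solicited reaction, including fever, per dose;
- any unsolicited AE, any MAAE and any SAE, each over its collection period, with the period named in the row.

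Specify that the interval is obtained by inverting the MN score test, with the restricted estimates re-evaluated at each candidate difference, and not by the formula printed in SAP 5.4.1. Inversion also gives a usable limit when neither arm has an event. State whether the pooled interval is crude or stratified, since randomization is stratified by country. Label the intervals descriptive and unadjusted for multiplicity.

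The cost is one column in existing tables and no new data. The list gives about (4 + 10) × 2 + 3 = 31 intervals: four composites and ten solicited reactions for each of two doses, plus three others. The downside is that this many unadjusted intervals could be over-read, which is why the list should stay short and carry the label.

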10.2 Adverse Events

An AE is defined as any untoward medical occurrence in a clinical investigation subject administered a trial vaccine; it does not necessarily have to have a causal relationship with trial vaccine administration. An AE is also defined as any untoward medical occurrence in a clinical investigation subject from the time they enter the trial.

All adverse event (AE) summaries will be ordered by alphabetical system organ class (SOC), and decreasing frequency of preferred term (PT) within SOC, in the active arm overall column. A subject who

has multiple events in the same SOC and PT will be counted only once in the subject counts but all events will be included.

10.2.1 Severity of Adverse Event

In summaries including severity, the following severity categories will be summarized: 'Mild', 'Moderate', 'Severe'. For the solicited AE of fever the following categories of severity will be summarized: '<38°C', '38-39°C', '39-40°C', '≥40°C'. Subjects who experience the same event multiple times will be included in the most severe category. Missing severities are not expected, however if these occur they will not be imputed but will be included in relevant summary tables under a missing category.

10.2.2 Relationship to Trial and Routine Vaccinations

In summaries including relationship to trial vaccination and routine vaccinations, the following relationships will be summarized: 'Not Related', 'Related'. Subjects who experience the same event multiple times will be included in the most related category. Missing relationships are not expected, however if these occur they will not be imputed but will be included in relevant summary tables under a missing category.

10.2.3 Solicited Adverse Events

The solicited safety parameters for this study are the injection site reactions of pain, erythema, induration and swelling and the systemic adverse events of drowsiness, irritability/fussiness, loss of appetite, fever (defined as body temperature greater than or equal to 38°C), vomiting and diarrhea.

Solicited reactions will be assessed 30 minutes after administration of each dose of trial vaccine, and then daily for 7 days (including the day of administration).

Body temperature measurements will be summarized in categories (including fever, defined as temperature $\geq 38^{\circ}\text{C}$), without adjustment for the route of measurement. Summaries of the day of first onset of each event and the maximum number of continuous days subjects experienced each event will also be provided.

Any solicited local or systemic reactions observed as continuing beyond 7 days following each trial vaccine dose will be recorded as an AE in the CRF.

Solicited AEs collected daily are entered in diaries by the participants Legally Acceptable Representative (LAR). The site investigator or designee will review the eDiary entries with the LAR and any data deemed to be implausible or incorrect may be updated during this review. The TFLs describe below will use the data entered by the LAR.

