9.3.3 Post Vaccination Procedures (Visits 1, 2 and 3)

After routine pediatric vaccine administration (Visit 1), the subject will be observed for at least 30 minutes including observation for AEs and body temperature measurement. Information should be recorded in the eCRF.

After trial vaccine administration (Visit 2 and Visit 3), the subject will be observed for at least 30 minutes including observation for unsolicited AEs, solicited local and systemic reactions and body temperature measurement. Information should be recorded in the eCRF.

The following post-vaccination procedures will be performed at Visit 2:

- The individual(s) who will enter the information into the eDiary will be trained on how to measure solicited local reactions and body temperature, how to complete the electronic diary card (eDiary) and how often to complete the eDiary. Training should be directed at the individual(s) who will perform the measurements of solicited local reactions (specifying that the RIGHT thigh must be evaluated) and those who will enter the information into the eDiary. This individual may or may not be the subject's LAR, but if a person other than the subject's LAR enters information into the eDiary, this person's identity must be documented in the source documents and this person must receive training on the eDiary. Training of the subject's LAR or these individuals on how to measure an injection site reaction, and how to take body temperature, and how to record the information in the eDiary, should be performed while the subject is under observation after trial vaccine administration.

eDiary instructions must include the following:

- The individual(s) who will enter the information into the eDiary must understand that timely completion of the eDiary on a daily basis is a critical component of trial participation.

Please note:

The eDiary will be the only source document allowed for remote collection of solicited local and systemic reactions and body temperature measurements. The following additional rules apply to the documentation of safety information collected by eDiary:

- The eDiary should be reviewed with the subject's LAR.
- No corrections or additions to the eDiary will be allowed after it is reviewed with the investigator/designee.
- Any data that are identified as implausible or incorrect and confirmed by the subject's LAR to be an error, should be corrected by the investigator/designee within the allowed review time.

CONFIDENTIAL

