10.2.3.1 Summaries

The summaries for solicited AEs will be:

- The number and percentage of subjects with solicited local and systemic reactions during the first 30 minutes after each dose of trial vaccine, overall and by severity.

- The number and percentage of subjects with solicited local and systemic reactions during the first 7 days (including day of administration) after each dose of trial vaccine, overall and by severity (Summaries will be for the time periods of 1-7, 1-3 and 4-7 days after trial vaccine)
- Daily summary of the number and percentage of subjects with solicited local and systemic reactions during the first 7 days (including day of administration) after each dose of trial vaccine overall and by severity
- Summary of the day of first onset of each solicited AE
- Summary of the number of days with each solicited AE within 7 days after each trial vaccination

A horizontal stacked bar plot showing the percentage of participants with each solicited AE, any solicited AE, any solicited injection site reactions, and any solicited systemic AEs after dose 1 and dose 2 will be presented. This plot will break down the percentages by maximum severity, with the percentage of mild, moderate and severe events stacked for each solicited AE.

All solicited AEs will also be listed.

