	A principal stratum strategy will be used to handle lack of compliance with vaccine administration schedule	Strategy change recommended by the FDA, no change to the planned handling of data in these cases.

14 SAP Amendment Details

The following changes were made to this document in version 2.0:

SAP Section	Summary of Change	Justification for Change
5.3.2.2	Table of LLOD's, LLOQ's and ULOQ's for immunogenicity parameters added.	To document the relevant ranges.

7.5.1	Added further clarity on the methods for calculating the differences in percentages and MH CIs using IPW.	For clarity.
	Added IPW approach if insufficient non-missing data are collected in participants with 1 trial vaccination.	To enable the calculation of adjusted proportions if the number of participants for any of t_1 to t_n are 0.
9.2.1.3	Updated supplementary immunogenicity estimands text to refer to secondary endpoints instead of primary endpoints.	Correction of typographical error.
10.2.3	Added paragraph clarifying that LAR data will be presented in TFLs for solicited AEs.	Agreed as the most appropriate approach following review of the available data.
All	A principal stratum strategy will be used to handle lack of compliance with vaccine administration schedule	Strategy change recommended by the FDA, no change to the planned handling of data in these cases.

15 References

[1] Clopper C, Pearson ES (1934). "The use of confidence or fiducial limits illustrated in the case of the binomial". *Biometrika*. 26 (4): 404–413.

[3] Seaman, Shaun R., and Ian R. White. "Review of inverse probability weighting for dealing with missing data." *Statistical methods in medical research* 22.3 (2013): 278-295.

Certificate Of Completion

Record Tracking

Signer Events

Signature

Timestamp

Signer Events

Signature

Timestamp

In Person Signer Events

Signature

Timestamp

Editor Delivery Events

Status

Timestamp

Agent Delivery Events

Status

Timestamp

Intermediary Delivery Events

Status

Timestamp

Certified Delivery Events

Status

Timestamp

Carbon Copy Events

Status

Timestamp

Witness Events

Signature

Timestamp

Notary Events

Signature

Timestamp

Envelope Summary Events

Status

Timestamps

Payment Events

Status

Timestamps

Electronic Record and Signature Disclosure

CONSUMER DISCLOSURE

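### Day 1–7 solicited-reaction tables use the caregiver's own diary entries, apparently including those later corrected as confirmed errors, and no planned output shows the corrected values

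*SAP*

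**What the plan says.** Protocol 9.3.3 makes the diary the sole source for what happens at home: "The eDiary will be the only source document allowed for remote collection of solicited local and systemic reactions and body temperature measurements". It also sets the correction rule. The rule opens "Any data that are identified as implausible or incorrect and confirmed by the subject's LAR to be an error, should be corrected by"; it then names the site's investigator or delegate, acting during the review period. The diary is closed to changes after that review.

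SAP 10.2.3 describes the same review more loosely: "any data deemed to be implausible or incorrect may be updated during this review". Its next sentence fixes the data source for the outputs: "The TFLs describe below will use the data entered by the LAR".

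SAP Section 14 logs this as a version 2.0 change: "Added paragraph clarifying that LAR data will be presented in TFLs for solicited AEs". The reason given is: "Agreed as the most appropriate approach following review of the available data".

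The main output affected is in SAP 10.2.3.1: "The number and percentage of subjects with solicited local and systemic reactions during the first 7 days (including day of administration) after each dose". It is given in total and split by grade. The daily, onset-day and duration summaries and the stacked severity plot draw on the same diary data. SAP 10.2.1 counts an infant with repeated episodes once, in the worst category.

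**The concern.** The review at the end of the diary week is the protocol's step for removing entry errors from the solicited data. If the outputs are built from what the LAR first typed, the result of that step is set aside. A temperature or millimetre value that the LAR has agreed was a slip would still be counted.

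Occurrence of solicited reactions by severity is the first safety endpoint listed in SAP 4.2.3. The trial is descriptive, so the reported percentages and grades are themselves the result. Categories such as 40°C and above, or more than 40 mm, may hold few infants, and there a handful of wrong entries would be visible. As the SAP stands, a reader of the report could not tell whether that had happened.

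**Working it through.** The plan states no figure for this point, so there is nothing to reproduce. The check is mainly of text, with some arithmetic for scale.

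**Which value is analysed?**

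1. Under protocol 9.3.3 a confirmed error "should be corrected by the investigator/designee within the allowed review time". The corrected value is therefore entered by the site, not by the LAR.
2. SAP 10.2.3 mentions updates at review and then names the LAR's entries as the source for the outputs. It does not say in so many words that an original entry is used where a corrected one exists. But if LAR data simply meant the diary after review, the sentence added in version 2.0 would settle nothing.
3. The output list in SAP 10.2.3.1 has no table on reviewed values, no count of changed entries, and no listing of original against corrected values. The general listing of solicited reactions is itself one of the outputs governed by the rule.
4. The 30-minute assessment is different. Protocol 9.3.3 has it observed at the site and recorded in the eCRF, so the issue is confined to the day 1–7 diary data.

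**What can one entry do?** Under the worst-category rule, a falsely high entry on any of seven days can set the infant's grade. A falsely low entry changes the grade only if it hides the true peak. The rule is thus more exposed to high errors, but the net direction depends on which errors occurred, and the documents do not report that.

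**Scale.** Arm size is 200 (SAP Section 6), so one infant is 1/200 = 0.5 percentage points. SAP 10.1.2 also presents safety by country. If the US enrolled only the target minimum of 100 (protocol 4.2) and the 1:1 allocation, stratified by country, gave 50 per arm, one infant would be 1/50 = 2 percentage points.

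**Illustration under assumed error rates.** Let e be the chance that a given infant-day carries an uncorrected false-positive entry for one reaction, independent across days. The chance of at least one in seven days is p = 1 − (1 − e)^7. A true rate of 2% would then be reported as 0.02 + 0.98p.

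| Assumed e | p | Expected infants of 200 | True 2% reported as |
|---|---|---|---|
| 0.1% | 0.7% | 1.4 | 2.7% |
| 0.25% | 1.7% | 3.5 | 3.7% |
| 0.5% | 3.4% | 6.9 | 5.4% |
| 1% | 6.8% | 13.6 | 8.7% |

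None of these error rates comes from the documents. The table shows only that a low daily error rate accumulates over seven days and matters most where the true rate is small.

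**The case against.** The strongest defence is that unedited caregiver reports, entered at the time, are protected from later changes by site staff, and the diary is the only permitted source for these data. That is a legitimate choice of main analysis, and it stands. The SAP does not argue it, however, and the protocol already limits site editing: corrections need the LAR's confirmation, and data collectors are blinded.

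A reader might infer an undeclared breach of the protocol. The documents do not support that. Section 14 of the SAP discloses the choice, and protocol 13.1.3, which governs the safety analysis, does not say which version is tabulated. What remains is that Section 13, which lists two other changes to the protocol, does not relate this choice to protocol 9.3.3.

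A reader might also infer a biased comparison between arms. LARs and data collectors are blinded (protocol 8.7), so there is no stated reason for errors to differ by arm.

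Nor do the documents show that errors dominate the severe categories. No error count is given, only four of the ten solicited items are measurements, and errors can lower a grade as well as raise it.

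There are partial safeguards. Under protocol 10.4.2, solicited reactions that are serious, lead to withdrawal, or last beyond seven days also go on the AE eCRF. These do not show what the review changed in the diary tables.

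**Conclusion.** The point holds for the day 1–7 diary outputs. On its natural reading the SAP tabulates entries that were confirmed as errors and corrected, and it plans no output on the corrected values. At the least, the analysis value is undefined wherever the two versions differ.

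The size is known only per infant: 0.5 percentage points in an arm of 200. The total effect and its direction are unknown, because the documents do not say how many entries were changed. What is at risk is the accuracy of absolute rates and severity grades, chiefly in sparse categories.

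The conclusion rests on reading LAR-entered data as data before site correction. If the sponsor meant the diary as it stood after review, one clarifying sentence would remove the inconsistency. The case is for a sensitivity analysis and a clear rule; it does not show that the main table must be switched to reviewed values.

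**What to change.** - In SAP 10.2.3, state which value is analysed when the LAR's original entry and the reviewed entry differ, and give the reason.
- Keep the LAR-entered tables as the main presentation if preferred, but repeat the day 1–7 by-severity tables on the reviewed values as a sensitivity analysis.
- Report the number of changed entries by arm, with a listing of original against corrected values.
- Note the choice against protocol 9.3.3 in SAP Section 13.

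The work is a rerun of existing table programs plus one count and one listing, provided both versions of each changed entry have been kept. The downside is a second version of these tables to produce and explain.
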